9.8. General flowchart of study

9.9. Randomization flowchart

9.10. Procedures flowchart

Visit number	V1	V2	V3	V4	V5	Vn
Day	D0	D1	Hasta 72h Postoperatori as	D7 a D12 Postoperator io	D42 Postoperator io	Visitas no programad as
Name of the visit	Selecció n	Aleatorizaci ón	Seguimiento 1	Seguimiento 2	Fin de Seguimiento	Seguimient o N
Activity						
Hospital admission	Х					Х
Inclusion and exclusion criteria	Х	Х				
Assignment of consecutive number (Screening)	Х					
Informed consent	X					
Demographic data	Х	Х				

Obstetrics						
and	Х	Х				
history						
Short						
Physical						
Examination		Х				
(Height and						
weight)						
Laparotomy /		v				
on		Λ				
Hydrostatic						
balloon						
uterine		Х	Х			
tamponade						
Characteristi						
cs of the		Х				
surgical						
Nouthorn						
vital status		v	x			
and weight		71	7			
Type of						
postoperative			V			
hospitalizatio			А			
n						
Complication			x	x	x	x
of surgery						
ICU			х	Х	х	х
admission						
Surgical			V	V	V	V
reinterventio			Х	Х	Х	Х
discharge			Х	Х	Х	Х
Evaluation						
Near Miss			x	х	х	х
Criteria						
Blood						
component			x	х	х	х
transfusion						
Arterial						
thrombosis						
associated			Х	Х	Х	Х
with vascular						
intervention						
11			77			
lleum			Х			
Supra fascial						
hematoma			Х			
Surgical						
wound				Х	Х	Х
infection						

Clavien Dindo Scale		Х	Х	Х	Х
Hospital discharge			Х	Х	Х
Adverse Events	Х	Х	Х	Х	Х
Telephone contact (Telemedicin e)				Х	

9.11. Operative aspects:

Eligible women will receive complete information about the study. If they agree to participate in it, they will sign the informed consent for both interventions: hysterectomy and partial myometrial resection. The final modality of intervention will be decided at randomization prior to the start of the surgical procedure.

The patients will undergo laparotomy with adequate anesthesia, the anesthesia method will be decided based on the pre-anesthetic evaluation and the mother's choice. During laparotomy, the clinical signs and the FIGO classification for PAS will be recorded¹⁷: Once the abdomen is surgically entered, the anterior aspect of the uterine segment is observed in detail (it is likely that a vesicouterine dissection will be required) and the diagnosis of PAS is confirmed (See Appendix 2, Definition of confirmed case of PAS).

If the diagnosis of PAS is ruled out (If the clinical criteria for PAS proposed by FIGO [Appendix 2] are not present), the patient is excluded from the study and subsequent surgical management will be defined by the treating surgical group.

If the diagnosis of PAS is confirmed by observing the clinical criteria endorsed by FIGO (Appendix 2), the patient's participation in the study is confirmed and the surgical procedure defined by randomization is continued, that is, one of the two arms of the study:

Primary hysterectomy: An incision will be made above the level of the placenta, delivering the newborn. Uterotonics will be administered, and spontaneous delivery of the placenta will be awaited using gentle traction. The absence of spontaneous separation of the placenta will confirm the diagnosis of PAS, the patient will undergo hysterectomy. The complete removal of the uterus will be attempted, including the cervix, the duration of the intervention and intraoperative blood loss will be recorded, as well as the damage to organs neighboring the uterus. In this arm of the study, hysterectomy will be performed in 100% of patients.

Partial myometrial resection: The technique described by Palacios-Jaraquemada et al⁵. will be followed. Briefly, the uterus will be dissected to free it from the posterior wall of

the bladder to the cervix. The vesico-uterine vessels will be ligated and the parametrial space will be visualized. The hysterotomy will be performed in the upper segment, immediately above the area of invasion of the myometrium. The entire invaded myometrium and the entire placenta will be removed. The uterus will repair itself in one or two layers. Intrauterine balloon tamponade will be used if indicated.

Post-operative care will be routine care according to the indication of the treating medical team.

To consult the detailed description of the interventions (hysterectomy and partial resection) and the procedures for the evaluation of clinical outcomes, see the standardized operating plan (See Appendix 4)

From the admission of the patient to the obstetric care unit until the end of the study follow-up process (42 days after the cesarean section), it will be evaluated whether the patient meets the criteria for extreme maternal morbidity (Consult the maternal morbidity surveillance protocol Extrema Cod: 549 of the National Institute of Health, available at: https://www.ins.gov.co/buscador-eventos/Paginas/Fichas-y-Protocolos.aspx) in case of meeting any of the inclusion criteria, the treating medical team will be in charge of filling out the individual notification form Cod. INS 549 for immediate reporting

In the same way, in the event of the death of a participant during the study period, due diligence of the individual notification form will be carried out for the maternal mortality event, INS Code 551 by the treating medical team.

9.12. Randomization:

There will be a randomization in a 1: 1 ratio in blocks of 4 and 6, stratified by each center. This process will be conducted by a statistician from the Fundación Valle del Lili Clinical Research Center independent of the research group, who will use a public access package: *Random Allocation Software* (http://www.msaghaei.com/Softwares/dnld/RA .zip) for that purpose.

The randomization sequence will rest in the *RED Cap*® software. Prior to the start of the surgical procedure, the clinical coordinator of the study will be asked to reveal the result of the randomization, once the presence of PAS is confirmed (See Appendix 2, confirmed case of PAS), the surgery will continue towards one of the two possible options (hysterectomy or partial myometrial resection). Participants and researchers will be informed of the intervention since it is an open-label clinical experiment.

9.13. Blinding:

This is an unblinded study as it is not possible to conceal the surgical procedure for each arm from the operator (Treating Physician) or from the participant.

The information of each patient will be consigned in electronic formats. In these, the therapeutic modality will not be expressly identified, in such a way that the independent statistician who will perform the analysis will also, in principle, not know the group to which each patient was assigned.

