	The name of the Clinical Coordinator of the study is modified, [name] [name] retires and [name] [name]
	joins the team.
	The description of the procedure for disclosure of randomization by the clinical coordinator is modified.
	Added role for the study coordinator to provide support to the PI in the collection of PAS prenatal diagnostic ultrasound photos and histology.
	The functions of the clinical coordinator of the study are adjusted, the figure of the sub-investigator is added.
Appendix 10: Standardized surgical technique manual and photographs	A detailed step-by-step description of both techniques to be implemented in the study and the technical specifications for taking photographs and videos are included in the surgical technique manual.

1. Introduction:

Placenta accreta spectrum (PAS) is an increasingly frequent pathology, which is probably related to the increased rates of cesarean sections throughout the world¹. This is a potentially dangerous condition associated with maternal risks, such as massive blood loss, pelvic organ damage (urinary tract or bowel), and occasional maternal mortality. Prenatal imaging detection was reported to have a high degree of accuracy in a cohort of women with an anterior cesarean delivery and placenta previa^{2,3}. However, both ultrasound and magnetic resonance imaging have variable diagnostic precision depending on who performs the study, reporting failures in both diagnostic modalities⁴. Thus, even a quarter of patients undergoing surgery for suspected PAS end up having another diagnosis⁵.

There are multiple management options, but the ideal treatment modality is unknown. The most widely used definitive treatment in the world is cesarean section - elective hysterectomy⁶. However, some investigators have reported that partial myometrial resection and uterine repair are successful in the vast majority of cases⁷.

Even though there are multiple publications about conservative surgical management techniques in different populations, one of them being the partial resection of the myometrium followed by uterine repair (a technique called resective reconstructive surgery), the international management guidelines for PAS only include this alternative as an option in selected cases. Probably due to the little diffusion of the technique and the

need for specific training in it. However, something similar happens with hysterectomy for PAS.

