Women with a previous cesarean section, anterior placenta previa, and imaging (ultrasound or MRI) with signs suggestive of PAS will be eligible to participate (See Appendix 2: Definition of a suspected PAS case). Informed consent will be requested from these patients prior to surgery. Considering that these are pregnant women, the participation of the husband or spouse will be included in the informed consent (Appendix 7). In the event that the patient does not have a husband or spouse, the "Declaration of mother head of the family" will be filled out (Appendix 8).

Randomization will be carried out before starting the surgical procedure, with the aim of reducing the possibility of selection bias by the surgical team since there is no blinding.

It is possible that some patients who are eligible before surgery and who have signed the informed consent, will cease to be eligible if macroscopic signs suggestive of PAS are not found at laparotomy (See Appendix 2: Definition of confirmed PAS case) (that is, if present a false positive result of the prenatal diagnostic images), which has been described in up to 22.6%¹¹ of the cases. These patients will be considered screening failures in the recruitment process and will be excluded from the statistical analysis.

9.5.1. Inclusion criteria:

- Pregnant women over 18 years of age.
- History of previous cesarean section and anterior placenta previa
- Patients with prenatal diagnosis by ultrasound or MRI of PAS (See Appendix
 2: Definition of a suspected case of PAS), regardless of the suspected degree of severity of the disease.
- Requirement for surgical management of placental accreta on a scheduled basis.
- Patients without active vaginal bleeding in the period immediately before surgery (Patients entering the operating room without active bleeding).

9.5.2. Exclusion Criteria:

- Women without previous living children.

9.6. Sample size:

As the aim of the study is not to compare the effectiveness between interventions, a formal power calculation was not performed. A sample size of 60 participants. According to the estimated recruitment rate for each center, the following distribution is proposed: 36 patients from Indonesia, 12 patients from Argentina and 12 patients from Colombia to address the feasibility objectives.

9.7. Recruitment strategy:

9.7.1. Participant selection:

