11.3. Conflict of interests

The researchers of this study declare that they have no conflicts of interest.

12. Report of adverse events:

The principal investigator of each center will be responsible for managing the safety of each participant and identifying adverse events related or not to the study interventions.

Adverse events should be recorded with the following information:

- Identification of the participant in the study.
- Time from randomization to occurrence of the event.
- Identification of the possible causal relationship between the event and the surgical intervention (hysterectomy or partial myometrial resection)
- Resolution or improvement of the adverse event.

12.1. Monitoring of adverse events:

All adverse events (AE) that occur within the first 42 days after randomization must be reported to the respective ethics committee following the guidelines for reporting serious adverse events (SAE), maintaining the confidentiality of the information. The SAE must be reported to the committee within the first 24 hours of the event.

12.2. Definition of adverse event: An Adverse Event (AE) is considered to be any adverse medical situation in a patient or subject of a clinical investigation who was

administered a pharmaceutical product or underwent a procedure and that does not necessarily have a causal relationship with this treatment. Therefore, an AE can be any unfavorable or unintended sign (including an abnormal laboratory finding), symptom or disease temporarily associated with the use of a medicinal product (research) or a certain intervention, whether or not it is related to it. product or intervention.

- Events that meet the definition of EA and their expected frequencies:
- Transfusions of more than 4 units of red blood cells (UGR):> 40%
- Bladder injury:> 60%
- Ureteral injury:> 30%
- Surgical wound infection:> 30%
- Complications related to intra-arterial balloons such as vessel thrombosis:> 30%

Events that DO NOT meet the definition of EA:

- Post-operative ileus
- Urinary retention
- Supra fascial hematoma
- Postpartum hemorrhage <2.5 L
- Expected daily fluctuations of pre-existing diseases or conditions present or detected at the beginning of the study that do not worsen.

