 - a. To perform laparotomy and before performing hysterotomy (opening the uterus), confirm the presence of clinical signs of PAS on the anterior surface of the uterus. The presence of the signs described by the consensus of the International Federation of Gynecology and Obstetrics (FIGO), described in Appendix 2, will be sought. Definition of confirmed case.
 - b. If the presence of clinical signs of PAS is confirmed, the patient continues in the study and the surgical procedure previously defined by the randomization process will be performed.
 - c. If the presence of clinical signs of PAS is ruled out, the patient is excluded from the study and subsequent surgical management will be defined by the group of treating surgeons.
- 9. Apply the selected surgical technique in the randomization process (hysterectomy or partial myometrial resection)

A. Total abdominal hysterectomy: An incision will be made above the level of the placenta, extracting the newborn. Uterotonics will be administered and spontaneous delivery of the placenta will be awaited using gentle traction. The absence of spontaneous separation of the placenta will confirm the diagnosis of PAS, the patient will undergo hysterectomy. The complete removal of the uterus will be attempted, including the cervix, the duration of the intervention and intraoperative blood loss will be recorded, as well as the injury to organs neighboring the uterus. In this arm of the study, hysterectomy will be performed in 100% of patients.

B. Partial myometrial resection: The technique described by Palacios-Jaraquemada et al.5 will be followed. Briefly, the uterus will be dissected to free it from the posterior wall of the bladder to the cervix. The vesico-uterine vessels will be ligated and the parametrial space will be visualized. The hysterotomy will be performed in the upper segment, immediately above the area of invasion of the myometrium. The entire invaded myometrium and the entire placenta will be removed. The uterus will repair itself in one or two layers. Intrauterine balloon tamponade will be used if indicated

10. Carry out the prospective collection of all clinical variables during surgery.

The objective measurement of the operative sac is the variable of greatest interest in a possible controlled clinical trial and requires special description since its correct measurement is basic for the analysis of results in both arms of the feasibility study and for the planning of a subsequent study.

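### Women ruled out at laparotomy are already randomised and fall under 42-day adverse event reporting (12.1), yet 9.11 and Appendix 5 exclude them from the study, so postoperative harm can be lost

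*Combined protocol and SAP*

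**What the plan says.** Section 9.4 fixes the order of events: "Randomization will be carried out before starting the surgical procedure, with the aim of reducing the possibility of selection bias by the surgical team". Sections 9.7.1 and 9.12 and principal investigator item 7 in Appendix 5 likewise have the coordinator reveal the allocation before the operation begins. PAS is confirmed or ruled out only after the abdomen is open. For that step, section 9.11 notes that "it is likely that a vesicouterine dissection will be required".

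If PAS is ruled out, section 9.11 says that "the patient is excluded from the study and subsequent surgical management will be defined by the treating surgical group". Appendix 5 item 8c gives the same rule: "If the presence of clinical signs of PAS is ruled out, the patient is excluded from the study". Section 9.4 classes these women as screening failures and removes them from the statistical analysis.

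The safety section counts from a different point. Section 12.1 states: "All adverse events (AE) that occur within the first 42 days after randomization must be reported". It makes no exception for women ruled out. Coordinator duty 14 in Appendix 5 asks for adverse event monitoring of every randomised subject. The assessments at which such events would be found (up to 72 hours, days 7 to 12, day 42) are written in section 10.2 for study participants.

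**The concern.** The woman is inside the safety rule, because she has been randomised, and outside the follow-up rule, because she has left the study. A centre working from 9.11 could properly close her record in theatre. A centre working from 12.1 would keep it open to day 42. Nothing in the text says which prevails.

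This matters more than the choice of analysis set. Leaving women out of an analysis can be reversed later, but data that were never collected cannot be recovered. The women concerned have had a laparotomy and possibly a pelvic dissection. Bladder injury, ureteral injury and wound infection are on the protocol's own adverse event list (12.2). Some of these can come to light only after the operation. A definitive trial that also randomises first and confirms PAS second would need to know how these women fare, and the feasibility study is where that can be learned.

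**Working it through.** **Step 1. The rules side by side, for a woman ruled out at laparotomy**

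| Source | Whom it covers | Effect on her |
|---|---|---|
| 12.1 | Adverse events within 42 days of randomisation | Reporting continues |
| Appendix 5, coordinator duty 14 | Each randomised subject | Monitoring continues |
| 9.11; Appendix 5 item 8c | Women with PAS ruled out | Excluded from the study |
| 10.2 | Study participants | No stated place for the 72-hour, day 7-12 or day-42 assessments |
| 9.4 | Women with PAS ruled out | Screening failure, not analysed |
| 10.6 | Women who withdraw consent | Says which contacts continue and which stop; there is no counterpart for her |

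The first two rows conflict with the third and fourth.

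**Step 2. What would be recorded anyway**

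The standard surgical note (Appendix 11) has a screening-failure field together with bladder, ureteral and intestinal injury, bleeding and transfusion. Harm recognised during the operation therefore has a place. Harm recognised later depends on the follow-up contacts in 10.2. The table shells in section 16 have a total column and two arm columns, so women ruled out have no place there even if data exist. The adverse event record in section 12 asks about causality only for the two study operations.

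**Step 3. How many women**

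Inputs:
- Sample size 60 (9.6). The site split 36 + 12 + 12 = 60 adds up. The plan has no formal calculation to reproduce.
- Share ruled out, f: section 9.4 says of false-positive imaging, "which has been described in up to 22.6"%, so 0.226 is a ceiling there. The Introduction says "even a quarter of patients undergoing surgery for suspected PAS end up having another diagnosis", so 0.25 is also shown. The value 0.20 is an assumed lower value.

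Formulas: if 60 are randomised, the number ruled out is 60 × f. If 60 confirmed cases are required, 60 / (1 − f) must be randomised, rounded up, and the excess over 60 is ruled out.

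| f | Ruled out of 60 randomised | Randomised for 60 confirmed | Ruled out |
|---|---|---|---|
| 0.20 | 12.0 | 75 | 15 |
| 0.226 | 13.56 | 77.52, so 78 | 18 |
| 0.25 | 15.0 | 80 | 20 |

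Chance alone also moves the count. With 60 randomised and f = 0.226, the central 95% binomial range is 8 to 20.

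**Step 4. How many events**

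The documents give no event rate for women without PAS; the expected frequencies in 12.2 are not broken down for them. As an assumption only, with 14 women and a true harm rate p, the chance of at least one event is 1 − (1 − p)^14: 25% at p = 2%, 51% at 5% and 77% at 10%. This is the chance that an event occurs, not that it goes unrecorded.

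**The case against.** The best defence is that the sections can be read together. On this view, exclusion in 9.11 means no randomised operation and no place in the analysis, as 9.4 describes, while 12.1 and coordinator duty 14 keep every randomised woman under adverse event reporting. That reading is reasonable and would give the right data. But 9.11 and Appendix 5 say excluded from the study without that limit, and 10.2 provides no contacts for her. The reading has to be written down.

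Several other points stand and limit the claim:

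- A reader might infer that the safety committee would see no harm data on these women. The documents do not support that: 12.1 still covers them on its face, and the surgical note captures injuries seen at operation.
- A reader might put a number on lost events. A 5-10% injury rate in 14 to 18 women gives 0.7 to 1.8 events, but that rate is assumed, and calling those events lost assumes that none would be recorded.
- The dissection is likely, not certain. Appendix 10 identifies findings at step 5, before the parametrial and retrovesical dissection of step 6, so it does not show that a woman ruled out undergoes step 6. Nor do the documents show that trial entry causes the surgery: inclusion requires that scheduled surgery is already needed, and section 14 says no surgical procedure is added to usual practice.
- The 22.6% is a ceiling, and section 2 attaches it to uteri removed without PAS. The Appendix 2 criteria for accreta, met by any one item, could leave fewer women ruled out.
- Differing practice between centres is possible, not shown. All three share one protocol and central monitoring.
- The flowcharts in 9.8 and 9.9 and the consent form are not in the text available here and may bear on the point.

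**Conclusion.** The contradiction is real and does not depend on any rate. A woman ruled out at laparotomy is owed 42 days of adverse event reporting under 12.1 and has no stated follow-up under 9.11, Appendix 5 item 8c and 10.2. The likely loss is partial and mainly postoperative: ureteral or bladder injury recognised late, reintervention, infection, death.

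The group at risk is up to about 14 of 60 randomised women, or about 18 of 78 if 60 confirmed cases are required, both at the 22.6% ceiling in 9.4. At the Introduction's figure of a quarter it would be 15 of 60 or 20 of 80. No count of missed events can be given. This should be corrected as an inexpensive improvement in harm capture; it does not make the feasibility design unsound.

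**What to change.** Reconcile sections 9.4, 9.11, 10.2 and 12.1 with item 8c and coordinator duty 14 of Appendix 5. State that a woman in whom PAS is ruled out:

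- does not continue to the randomised intervention and is counted as a screening failure;
- stays under adverse event recording, with contacts V3, V4 and V5 kept to day 42;
- has her safety data listed separately from the two arm columns and passed to the safety committee.

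The change concerns data collection and reporting only. Surgical management remains with the treating group, as the protocol already says.

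The cost is an amendment to the wording and, at the 22.6% ceiling, up to about 14 to 18 extra sets of follow-up entries and day-42 calls by existing staff. Consent is obtained before surgery, but the sponsor should check that the form in Appendix 7 covers follow-up after PAS has been ruled out.
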